5.1 Patient-level Study Calendar

[Patient-level study calendars for practices randomized to Arms 2 and 3 are provided are Appendices III and X.]

	Screening	Baseline*	Day of Surgery	8 weeks following surgery	12 weeks following surgery
Collected for all eligible (screened) patients					
Postoperative complications and outcomes				X (1)	X (1)
Adverse Event Assessment			X (1)		
Administered to all consenting patients					
Laboratory Studies					
HgB, WBC, Platelets		X		X***	
Serum creatinine		X		X***	
Serum albumin		X		X***	
Tests & Observations**					
ECOG PS		X		X***	
CHAMPS and EQ-5D Qx		X		X***	

* At initial surgical consultation. Questionnaires may be completed at any time following consent, before or after registration. Additionally, sites may leverage satellite NCORP locations to obtain baseline and 8-week follow-up labs and forms.

** Site staff may contact participants via email, U.S. mail, telephone and/or telehealth to administer and obtain questionnaires and assessments, including the CHAMPS Survey and the ECOG Performance Score.

*** Post surgery visits can be +/- 7 days

1. For the purposes of collecting and reporting adverse events into the Alliance database using Rave “adverse events” are those potentially resulting from intervention occurring between baseline and surgery. “Surgical complications” will be assessed 8 and 12 weeks after surgery using the Clavien-Dindo Classification. All CTEP-AERS events should be reported as outlined in [Section 9.0](#).

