12.4 Analysis plan

12.4.1 To assess the balance in randomization, baseline characteristics captured at the patient-level including age, gender, race, ethnicity, disease type, comorbidities, CHAMPS, EQ-5D-5L index and EQ-5D-5L visual analog scale will be compared across randomization arms using a generalized linear mixed model using the appropriate link function based on the distribution of the variable with a random practice effect to account for clustering within practice. Given the small number of sites, comparison of practice characteristics (e.g., practice volume; payer mix; solo, single specialty, or multi-specialty group practice; availability of geriatric specialists, palliative care providers, advanced practice providers,

patient navigators, on site occupational and physical therapy, social workers, pharmacists, dietetics, integrative medicine) across randomization arms will be descriptive.

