12.4.2 Primary analysis

The primary analysis will employ a generalized linear mixed model (with Gaussian link function) with a random practice effect to account for clustering within practice and baseline CHAMPS as a covariate to compare 8-week CHAMPS between the combined OPTI-Surg no-coach and coach arms versus usual care. This analysis will include all eligible elderly patients who undergo major cancer surgery, consent to complete CHAMPS questionnaires, and have baseline and 8-week function measured. In supplemental analysis, we will compare pairwise between arms (coach vs usual care, no-coach vs usual care, and coach vs no-coach) using the same method. Supplemental analyses will include model-based analysis with covariates from patient and practice characteristics which appear to differ among randomization arms.

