12.4.3 Secondary and exploratory analysis

A generalized linear mixed model (with logit link function) with a random practice effect to account for clustering within practice will be used to compare postoperative complications within 12 weeks of surgery between the combined OPTI-Surg no-coach and coach arms versus usual care followed by pairwise comparisons. This analysis will also include all eligible elderly patients who undergo major cancer surgery (no documentation of postoperative complications will be considered as not having any postoperative complications). A generalized linear mixed model (with logit link function) with a random practice effect to account for clustering within practice will also be used to compare compliance rate for screening between the no-coach and coach arms. This analysis will include all eligible elderly patients with planned major cancer surgery. Generalized linear mixed models (with appropriate link function based on the distribution of the outcome variable being compared) with a random practice effect to account for clustering within practice will be used to compare other surgical outcomes within 12 weeks of surgery and to compare EQ-5D-5L index and visual analog scale scores between the combined OPTI-Surg no-coach and coach arms versus usual care. Models for EQ-5D-5L scores will include the respective baseline EQ-5D-5L score as a covariate. In supplemental analysis, we will compare outcomes and EQ-5D-5L index and visual analog scale scores pairwise between arms (coach vs usual care, no-coach vs usual care, and coach vs no-coach) using the same method. Supplemental analysis will also incorporate patient and practice characteristics which appear to differ among randomization arms.

A variety of supplemental and exploratory analyses will be conducted primarily using descriptive analysis as well as model-based analysis (where applicable and supported by adequate sample size) including to describe the frequency of interventions implemented and to explore the relationship between site characteristics and likelihood of compliance.

With the addition of the virtual EFS effective with Update #03 to the study, we will additionally explore whether outcomes differed according to EFS used (in-person vs. virtual).

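### The primary model omits the stratification factor and other scheduled baseline variables, and the only further adjustment picks covariates by observed imbalance

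*Combined protocol and SAP*

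**What the plan says.** Section 12.4.2 defines the primary analysis as a mixed model "with a random practice effect to account for clustering within practice and baseline CHAMPS as a covariate to compare 8-week CHAMPS" between the two OPTI-Surg arms pooled and usual care. No other covariate is named.

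Practice type (thoracic, major abdominal, urologic) stratifies the randomization (Sections 4.3.2, 4.6 and 7.4). Section 1.5 gives the reason: recovery of function is expected to differ by type of procedure.

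Further adjustment appears only in supplemental analyses. Section 12.4.2: "Supplemental analyses will include model-based analysis with covariates from patient and practice characteristics which appear to differ among randomization arms". Section 12.4.3, for the other outcomes: "Supplemental analysis will also incorporate patient and practice characteristics which appear to differ among randomization arms". Neither gives a list, a threshold or a selection procedure.

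The judgement of difference comes from Section 12.4.1. There "age, gender, race, ethnicity, disease type, comorbidities, CHAMPS, EQ-5D-5L index and EQ-5D-5L visual analog scale will be compared across randomization arms" by mixed models, while the comparison of practice characteristics "across randomization arms will be descriptive".

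The calendar in Section 5.1 schedules ECOG performance status and "Serum albumin" at baseline under the heading "Administered to all consenting patients". Neither variable is named in 12.4.1 or in any model.

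**The concern.** A covariate is worth adjusting for because it predicts the outcome. A rule based on apparent imbalance can pass over a good predictor with a moderate imbalance and admit a weak one with a larger imbalance. With no threshold, and with practice characteristics judged by eye, the adjusted model is undefined until the data are seen. It then serves poorly as a sensitivity analysis.

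Prognostic imbalance is a real possibility here. Practices are randomized first and patients are consented afterwards, and only about 10 of the 30 practices are usual care. The plan itself treats frailty as prognostic: Section 12.3 assumes usual-care means of 8 kcal in frail and 18 kcal in non-frail patients. On those means, a 10-point difference between arms in the share of frail patients shifts the expected contrast by 0.10 × 10 = 1.0 kcal. That is 1.0/7.63 = 13% of the planned effect, before baseline CHAMPS absorbs part of it. The table of contents labels the frailty scale as for Arms 2 and 3 only, so frailty itself apparently cannot be a covariate. ECOG status and albumin are plausible stand-ins (my inference).

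At stake are precision and a defined adjusted analysis, not the validity of the primary test.

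**Working it through.** **Inputs (Sections 12.1 and 12.3).** 30 practices × 11 = 330 evaluable patients, allocated 1:1:1, so 220 v 110. SD 18.3 kcal, intracluster correlation 0.005, two-sided alpha 0.05. Stated power is 90%, 80% and 70% at effects of 0.42, 0.36 and 0.33. Non-binding futility at half information if p ≥ 0.323.

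**1. Reproduce the plan's figures.**
- Means: usual care 0.59×8 + 0.41×18 = 12.10. OPTI-Surg at 70% average screening is 19.73. Difference 7.63, and 7.63/18.3 = 0.417.
- Design effect 1 + (11−1)×0.005 = 1.05.
- SE in SD units: √[1.05×(1/110 + 1/220)] = 0.1197.
- Expected z: 0.42/0.1197 = 3.51; 0.36/0.1197 = 3.01; 0.33/0.1197 = 2.76.
- Fixed-sample power at 0.42 is 93.9%.
- Count a futility stop as failure: p = 0.323 two-sided is z = 0.988. Power = P(Z₁ > 0.988 and Z₂ > 1.960), where Z₁ has mean √0.5 × expected z and correlation √0.5 with Z₂. Result: **89.9%, 79.6%, 72.5%**. With a t critical value on 28 df at the final look: 89.1%, 78.0%, 70.5%.

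The stated 90/80/70 is recovered with no variance reduction from any covariate.

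**2. Add fixed covariates.** Replace SD by SD×√(1−R²), where R² is the assumed share of the remaining variance that the added covariates explain.

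| R² (assumed) | effect 0.42 | 0.36 | 0.33 |
|---|---|---|---|
| 0 | 89.9% | 79.6% | 72.5% |
| 5% | 91.2% | 81.5% | 74.6% |
| 10% | 92.5% | 83.5% | 76.8% |
| 20% | 94.9% | 87.4% | 81.4% |

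R² = 10% is worth 330/0.90 − 330 = 37 evaluable patients.

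This treats 18.3 as the SD left after baseline CHAMPS. If 18.3 is the raw SD and baseline CHAMPS correlates 0.5 with the outcome (assumed), expected z at 0.36 becomes 3.01/√0.75 = 3.47. Power then starts at 89%, and R² of 5–20% takes it to 91–95%. The gain is smaller but in the same direction.

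**3. What practice type alone could add.** At the plan's correlation of 0.005, suppose practice type explained all between-practice variance. The factor 1.05 would fall to 1 − 0.005 = 0.995, a cut of 1 − 0.995/1.05 = 5%, which is about the 5% row. Larger gains must come from patient-level variables (procedure group, age, ECOG status, albumin), or from a between-practice correlation above 0.005.

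**4. Compare selection on imbalance with a fixed set.** Simulation assumptions: 30 practices of 11, four prognostic covariates with intracluster correlation 0.05, selection at p < 0.10 (the plan has no threshold), t test on practice means, no futility stop, 4,000 runs.

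| Analysis | Type I error, R² 10% / 30% | Power at 0.33, R² 10% / 30% |
|---|---|---|
| No added covariates | 5.9% / 4.6% | 75% / 71% |
| Selected on imbalance | 5.2% / 3.7% | 76% / 74% |
| All four fixed | 6.0% / 5.2% | 82% / 89% |

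The Monte Carlo error on type I error is √(0.05×0.95/4000) = 0.3 points. Selection on imbalance does not inflate type I error, but recovers only 1 to 3 points of power against 7 to 18 for the fixed set.

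**The case against.** The strongest defence is that the primary test is already sound. Its model is fixed in advance and contains the baseline value of the outcome, usually the most useful single covariate. The imbalance rule touches only analyses labelled supplemental. This stands. A reader might infer that the primary covariate set can be chosen after seeing results, or that its type I error is inflated. Section 12.4.2 does not support either reading.

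The other objections:
- **No figure shows that the omitted variables are strong predictors.** Correct; the gain can only be given as a range. Practice type rests on firmer ground, because Section 1.5 states why it matters.
- **The list in 12.4.1 is illustrative.** Correct: ECOG status and albumin are unnamed rather than excluded, and age and disease type could enter a supplemental model. That still leaves entry to judgement after the data are seen.
- **A false-flag rate cannot be computed.** A reader might take nine characteristics at 5% and obtain 1 − 0.95⁹ = 37%. The plan states no threshold, the nine are not independent, and baseline CHAMPS is already in the model. I place no weight on that figure.
- **Data may be missing.** The schema requires no initial lab values. The Arm 2 and 3 calendars are in Appendices III and X, which I did not have, so collection there rests on the main calendar. If 10% of patients were dropped for missing albumin, 330×0.90/(1−0.10) = 330, and the gain at R² = 10% disappears. The fix must therefore drop no one.
- **Complications cannot simply be adjusted at patient level.** Section 13.1.1 says that data on non-consenting patients are collected in aggregate. This stands and limits the fix.

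**Conclusion.** The point holds as an inexpensive improvement in precision and prespecification. The primary model omits the stratification factor, for which the plan gives a prognostic reason, and other baseline variables the trial already schedules. The only route to further adjustment is a rule that selects on imbalance, is not defined in advance and gains little.

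Power at an effect of 0.36 would rise from about 80% to 82–87%, if the added covariates explain 5% to 20% of the variance left after baseline CHAMPS. That range is my assumption. The gain is smaller if 18.3 kcal is the SD before baseline adjustment.

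A reader might go further and conclude that the 90% power or the sample size is wrong. It is not: the stated figures reproduce without any added covariate.

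**What to change.** Make these changes before any outcome comparison by arm, including the futility look.

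- **12.4.2, primary model:** besides baseline CHAMPS, include practice type (or procedure group) and age as fixed covariates, whatever their balance. Put baseline ECOG status and albumin in the same model or in one named sensitivity model.
- **Missing baseline values:** state a simple rule for the added covariates, such as single imputation pooled over arms, so that no patient leaves the analysis.
- **12.4.3:** use the same set for the EQ-5D-5L scores, with their own baseline. For complications use practice type; add patient-level age and procedure only if the data held under 13.1.1 allow it.
- **Supplemental analyses in 12.4.2 and 12.4.3:** replace the clause on apparent differences between arms with this fixed list. Deleting the clause alone would leave the set open.
- **12.4.1:** keep as description only.

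The cost is SAP wording, handling of missing labs and a few degrees of freedom. Practice type takes two at practice level, from 30 − 2 = 28 to 26. No new data collection is needed if Arms 2 and 3 follow the main calendar.

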12.4.3 Secondary and exploratory analysis

A generalized linear mixed model (with logit link function) with a random practice effect to account for clustering within practice will be used to compare postoperative complications within 12 weeks of surgery between the combined OPTI-Surg no-coach and coach arms versus usual care followed by pairwise comparisons. This analysis will also include all eligible elderly patients who undergo major cancer surgery (no documentation of postoperative complications will be considered as not having any postoperative complications). A generalized linear mixed model (with logit link function) with a random practice effect to account for clustering within practice will also be used to compare compliance rate for screening between the no-coach and coach arms. This analysis will include all eligible elderly patients with planned major cancer surgery. Generalized linear mixed models (with appropriate link function based on the distribution of the outcome variable being compared) with a random practice effect to account for clustering within practice will be used to compare other surgical outcomes within 12 weeks of surgery and to compare EQ-5D-5L index and visual analog scale scores between the combined OPTI-Surg no-coach and coach arms versus usual care. Models for EQ-5D-5L scores will include the respective baseline EQ-5D-5L score as a covariate. In supplemental analysis, we will compare outcomes and EQ-5D-5L index and visual analog scale scores pairwise between arms (coach vs usual care, no-coach vs usual care, and coach vs no-coach) using the same method. Supplemental analysis will also incorporate patient and practice characteristics which appear to differ among randomization arms.

A variety of supplemental and exploratory analyses will be conducted primarily using descriptive analysis as well as model-based analysis (where applicable and supported by adequate sample size) including to describe the frequency of interventions implemented and to explore the relationship between site characteristics and likelihood of compliance.

With the addition of the virtual EFS effective with Update #03 to the study, we will additionally explore whether outcomes differed according to EFS used (in-person vs. virtual).

12.4.4 Missing data

We first plan to minimize missing data prospectively through use of central data collection in Rave within the Alliance Statistics and Data Center with prospective monitoring of data consistency and completeness. Prospectively, we also plan a staged roll-out with monthly contact with practices to identify missing data problems early. Analytically, for the primary

analysis we will first compare baseline characteristics (age, gender, race, ethnicity, cancer surgery type) among the eligible elderly patients who undergo major cancer surgery with and without 8-week CHAMPS data. We next plan to use all observations available for the initial analysis followed by incorporation of propensity scores in weighted regression in supplemental analysis (assuming there are systematic differences observed in patients with and without missing data). We will also employ a variety of single and multiple imputation methods and results will be descriptively compared across all methods to assess for impact of assumptions on results. In the event of more than 30% missing data for the primary endpoint, we will focus the analysis primarily on the key secondary endpoint of postoperative complications as we expect relatively complete data for this endpoint.

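### The check for informative missingness of 8-week CHAMPS uses five variables, none a measure of function or frailty, and weighting depends on that check finding a difference

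*Combined protocol and SAP*

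**What the plan says.** Section 12.4.4 starts with a comparison of patients who do and do not have 8-week CHAMPS: "we will first compare baseline characteristics (age, gender, race, ethnicity, cancer surgery type". Nothing in the wording suggests that the list is illustrative. An analysis of available data follows, then "incorporation of propensity scores in weighted regression in supplemental analysis", on the condition "assuming there are systematic differences observed in patients with and without missing data". No threshold defines a systematic difference, and the propensity covariates are not named. The section continues "We will also employ a variety of single and multiple imputation methods", with results compared descriptively; no imputation predictors are named. It also has a fallback, "In the event of more than 30% missing data for the primary endpoint", under which emphasis moves to postoperative complications.

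The primary analysis (12.4.2) is restricted to consenting surgical patients who "have baseline and 8-week function measured". It has a random practice effect and baseline CHAMPS as its covariate.

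The calendar in 5.1 lists ECOG PS, haemoglobin, creatinine, albumin, CHAMPS and EQ-5D at baseline in the block headed "Administered to all consenting patients". Section 10.3.1 records complications, length of stay and readmission. For balance between arms, 12.4.1 uses a longer list than 12.4.4: it adds disease type and comorbidities, and "CHAMPS, EQ-5D-5L index and EQ-5D-5L visual analog scale will be compared across randomization arms".

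**The concern.** A missingness check can reveal only what its variables carry. Section 12.3 makes frailty the main driver of both outcome and benefit: frail patients score 8 unscreened and 23 screened (gain 15), non-frail patients 18 and 23 (gain 5). If frailer patients return fewer week-8 questionnaires, the complete cases over-represent patients with less to gain. Age, gender, race, ethnicity and surgery type need not show this. The check would then look clean and the weighted analysis would not be run.

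The sample size allows for 11 evaluable of 15 enrolled per practice, so 4/15 = 26.7% missing is planned for. That is just below the 30% level at which emphasis shifts to complications, so the CHAMPS comparison would go ahead with about a quarter of outcomes missing. The plan also applies a richer covariate list to arm balance than to missingness.

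**Working it through.** **1. The plan's own figures (12.3).** Average screening is (60% + 80%)/2 = 70%.
- OPTI-Surg, frail: 0.7×23 + 0.3×8 = 18.5. Non-frail: 0.7×23 + 0.3×18 = 21.5. Overall: 0.59×18.5 + 0.41×21.5 = 19.73.
- Usual care: 0.59×8 + 0.41×18 = 12.10.
- Difference 7.63; 7.63/18.3 = 0.417, stated as 0.42.
- Design effect 1 + (11−1)×0.005 = 1.05, as stated.
- Power with 110 versus 220 evaluable patients at 0.42 is 93.9% by the plain normal formula, and 89.9% if the futility rule is followed. The stated 90% reproduces.

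**2. Complete-case difference when dropout depends on frailty.** Let m be overall missingness and r the frail to non-frail dropout ratio; r is assumed, as the documents give none. Non-frail dropout is d = m/(0.59r + 0.41) and frail dropout is rd. The frail share of observed patients is p = 0.59(1 − rd)/(1 − m). Observed means are 18 − 10p (usual care) and 21.5 − 3p (OPTI-Surg).

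Example, m = 0.267 and r = 3: d = 0.267/2.18 = 0.122, rd = 0.367, p = 0.59×0.633/0.733 = 0.509. Usual care is 12.91, OPTI-Surg 19.97, difference 7.06.

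| m | r | Both groups | Usual care only | OPTI-Surg only |
|---|---|---|---|---|
| 26.7% | 2 | 7.24 | 7.08 | 7.80 |
| 26.7% | 3 | 7.06 | 6.82 | 7.87 |
| 30% | 2 | 7.17 | 6.98 | 7.83 |
| 30% | 3 | 6.96 | 6.68 | 7.92 |

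In the last two columns the other group loses the same fraction at random. Against 7.63, the first two columns are 5% (7.24) to 12% (6.68) too small, and the last is 2% (7.80) to 4% (7.92) too large. With 330 evaluable patients, plain-formula power at 7.63 is 93.6%; over the first two columns it is 86% to 91%. These figures are not adjusted for baseline CHAMPS.

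**3. Would the check see it?** Simulation of 450 patients in 30 practices at 26.7% missing, 600 runs per scenario. Assumptions not in the documents: a difference counts as observed if any single test gives p < 0.05; three baseline proxies (standing in for measures such as ECOG PS, albumin and EQ-5D) correlate 0.5 or 0.7 with a latent frailty score; age correlates 0 or 0.2 with it; baseline CHAMPS correlates about −0.3 with it.

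| Dropout pattern | Five-variable check flags | Proxies plus baseline CHAMPS flag |
|---|---|---|
| Completely random | 17–22% | 15–17% |
| Ratio 2, both groups | 20–24% | 67–84% |
| Ratio 3, both groups | 20–33% | 93–97% |
| Ratio 3, usual care only | 19–23% | 35–42% |

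The five-variable check flags frailty-driven dropout little more often than pure chance.

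**4. Would weighting correct it?** With baseline CHAMPS in the model, complete-case estimates under frailty-driven dropout were 6.87 to 7.29. Weighting on age, gender, race and surgery type (ethnicity omitted, since only 9 of 450 planned patients are Hispanic) changed them by at most 0.02. Adding the proxies and baseline CHAMPS moved them 0.07 to 0.29 towards 7.63, giving 7.05 to 7.41. Under random missingness the complete-case estimates were 7.58 to 7.68, which indicates the simulation noise.

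**The case against.** Much of the case on the other side stands.

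- A reader might infer that frailty-driven dropout goes uncorrected. The text does not support that. Imputation is not tied to the check, and baseline CHAMPS in the primary model absorbs dropout explained by baseline function. What remains is that the imputation predictors are unnamed, so imputation is not a specified safeguard.
- A reader might infer that the weights would use only the five variables. The list governs the comparison; the propensity covariates are simply unspecified.
- A reader might take it as established that frail patients, or those with complications, return fewer questionnaires. No section says so, and 5.1 permits collection by email, post, telephone or telehealth. The dropout ratios above are assumptions.
- The short list may have a reason. Section 12.4.4 refers to eligible patients who undergo surgery without mentioning consent, and 13.1.1 limits data on non-consenting patients to aggregate items such as demographics, surgery type and complications. ECOG PS, the laboratory values, CHAMPS and EQ-5D are scheduled for consenting patients only. A wider check must be confined to them, but they are the primary analysis population.
- Complications are not baseline characteristics, they are followed to 12 weeks, and Clavien-Dindo grade V is death. They cannot simply be added to the list.

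**Conclusion.** The point holds as a weakness in how the missing-data sensitivity analyses are specified. It does not show that the primary model is wrong. As written, the check is close to blind to dropout related to frailty or performance status, and a clean result switches off the weighted analysis.

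The size is modest: from 12% below to 4% above the planned 7.63 before adjustment for baseline CHAMPS, under assumed dropout ratios of 2 to 3 and the frail and non-frail means in 12.3. It would be wrong to conclude that the plan is biased against OPTI-Surg, because loss of frail patients in the OPTI-Surg arms alone inflates the difference. Nor does a wider predictor set remove the bias: in the simulation it recovered part, and detection was only 35–42% when usual care alone was affected. The case for change is that the predictors are already collected and can be fixed before outcomes are seen.

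**What to change.** Amend 12.4.4 as follows.

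1. Define the comparison population as consenting patients who undergo surgery. Keep the five variables and add arm, comorbidities, baseline CHAMPS, baseline EQ-5D, ECOG PS, albumin, haemoglobin and creatinine.
2. Name this set as the predictors in both the propensity-weight and the imputation models. Add practice, and complications, readmission and length of stay occurring before the week-8 assessment. These post-operative variables predict missingness; they do not belong in the baseline comparison or as covariates in the outcome model.
3. Run the weighted sensitivity analysis in all cases and delete the condition that differences be observed.
4. Treat deaths before week 8 separately, so that survivors are not weighted to represent patients who could not have had a score. For example, model missingness among those alive at the assessment and report deaths by arm alongside.

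Cost: SAP wording, a little more analysis work and a simple rule for missing baseline laboratory values. With about 120 missing outcomes expected (450 − 330), a longer predictor list may make the weights more variable, so their distribution should be reported. No new data are needed.
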